9.2.3 SECONDARY ANALYSES

All secondary endpoints will be analysed using the SFAS.

Other subgroup analyses maybe carried out, these will be defined prior to database lock.

NOTE: Although a subject will be included in the analysis set regardless of their sequence of treatment, only data collected while a subject was on tofacitinib will be included in the secondary analyses. Methods used are described in Section 9.1.2 - 9.1.4.

9.2.3.1 TIME TO FIRST TREATMENT ESCALATION

Time to first treatment escalation will be analysed as in Section 9.1.2 using the SFAS. Missing or incomplete dates will not be imputed (as per Section 8.1).

9.2.3.2 RATE OF LDA

Each definition of LDA (Section 7.1.2.2) will be presented as in Section 9.1.4, using the SFAS, only including data when patients were taking tofacitinib. Missing data will not be imputed (as per Section 8.2).

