7.12. Limitations of the research methods

Randomised controlled trials are important and powerful tools in assessing efficacy and safety but have their limitations in terms of generalisability. In order to assess health economics, clinical effectiveness and safety of Tofacitinib in a usual care setting, parameters need to be determined by performing observational studies.

Inherent limitations of non-interventional, observational, non-controlled, non-randomised studies in general are the risk of selection/ascertainment bias and some lack of a parallel control group, which complicate the interpretation of the causality between treatment and outcomes. Furthermore, as with any "as observed" analysis, there is a potential risk of bias due to missing outcome data; the risk increases with increasing number of missing outcome data.

As data captured will be limited to information available from the physician participating in the study under a usual care setting, there is a greater possibility that there will be individual items of missing data (e.g. CRP not measured or FFbH questionnaire not completed). Following up patients after treatment escalation, rather than discontinuing patients from the study when they switch from Tofacitinib, should result in a higher proportion of the patients remaining in the study until the planned completion date. Where data are missing, information from the patient at other visits may be used in the primary analysis model to assess predictors of treatment decisions. If the different factors being considered in the primary statistical model to look at impact of treatment change are highly correlated it may not be clear which of the factors is in fact driving the rate of treatment escalation. Other sensitivity analyses may be explored to assess the impact of any confounding. Further details will be included in the SAP.

Patients selected for study inclusion represent a population who are initiated on Tofacitinib as part of a usual care setting. The sample of patients will be obtained from physicians who are willing to participate in the study and there is a possibility that certain types of patients will be selected to be prescribed Tofacitinib (selection bias) and join the study and this could potentially have an impact on findings of the primary analysis (if the 'type' is expected to impact the rate of treatment escalation). Therefore, study findings may not be generalizable to all RA patients.

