6.3 SECONDARY FULL ANALYSIS SET

Patients with data collected while taking tofacitinib will be assigned to the Secondary Full Analysis Set (SFAS) at a given time point, which will be used for all secondary endpoint analyses. A patient is considered on tofacitinib at a given timepoint if the patient has not terminated or paused tofacitinib at the time of the visit or event. Termination or pauses are documented in eCRF instrument “Rheumatologische Medikation” for therapy class tsDMARD/bDMARD, where variable *Change* (BDCM.CHANGECD) is set to “Therapy stop” = termination or set to “Therapy paused” = pause.

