7.1.2.2.1 SDAI LDA

At each time point (M3, M6, M9, M12, M15, M18, M21, M24) SDAI LDA is derived as:

$$\begin{aligned} \text{SDAI_LDA} &= 1 \text{ if} & \text{SDAI} &\leq 11 \\ \text{SDAI_LDA} &= 0, & \text{otherwise.} \end{aligned}$$

The proportion of patients in SDAI LDA at Month X is then calculated as:

No. of patients with SDAI LDA at Month X / Total Number of patients with non-missing SDAI LDA at Month X.

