7.1.2.2.3 DAS28-4 (ESR) LDA

At each time point (M3, M6, M9, M12, M15, M18, M21, M24) DAS 28-4 (ESR) LDA is derived as:

$$\begin{aligned} \text{DAS 28-4 (ESR) LDA} &= 1 \text{ if } \text{DAS 28-4 (ESR)} \leq 3.2. \\ \text{DAS 28-4 (ESR) LDA} &= 0, \quad \text{otherwise.} \end{aligned}$$

DAS28-4 (ESR) is calculated as in Section 7.1.2.4.1

The proportion of patients in DAS 28-4 (ESR) LDA at Month X is then calculated as:

No. of patients with DAS 28-4 (ESR) LDA at Month X / Total Number of patients with non-missing DAS 28-4 (ESR) LDA at Month X.

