9.1.4 ANALYSIS FOR BINARY DATA

Binary data will be presented using counts and percentages. To calculate the percentage, the denominator will be the number of subjects with a non-missing value. These will be presented for each time point.

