9.2.3.3 RATE OF REMISSION

Each definition of Remission (Section 7.1.2.3) will be presented as in Section 9.1.4, using the SFAS, only including data when patients were taking tofacitinib. Missing data will not be imputed (as per Section 8.2).

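### LDA and remission rates are taken only among patients still on tofacitinib with a score, so their trend over time cannot be read as the course of response in patients who start the drug

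*SAP*

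**What the plan says.** Protocol Section 6.1.2 (items b and c) defines the LDA and remission rates over time for patients on tofacitinib, alone or in combination. The SAP carries this through in three steps.

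- **Who is in the set.** Membership of the Secondary Full Analysis Set (SFAS) is decided at each time point. A patient counts as on the drug "if the patient has not terminated or paused tofacitinib at the time of the visit or event" (SAP 6.3). SAP 9.2.3 adds that "only data collected while a subject was on tofacitinib will be included in the secondary analyses".
- **What is reported.** LDA is presented "using the SFAS, only including data when patients were taking tofacitinib" (SAP 9.2.3.2). SAP 9.2.3.3 applies the same rule to remission: "Each definition of Remission (Section 7.1.2.3) will be presented as in Section 9.1.4, using the SFAS", again with on-drug data only.
- **The denominator.** For LDA by SDAI it is the "Total Number of patients with non-missing SDAI LDA at Month X" (SAP 7.1.2.2.1). The other LDA and remission definitions are built the same way, and SAP 9.1.4 states the general rule: "the denominator will be the number of subjects with a non-missing value". Missing binary values are not imputed (SAP 8.2).

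The summary table in SAP 9.2.6 labels these rows FAS rather than SFAS but keeps the on-drug restriction. Protocol 7.9.1 (Analysis Populations) names the FAS for all efficacy analyses. Neither document plans an LDA or remission rate with a fixed denominator.

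**The concern.** A patient who stops tofacitinib leaves the numerator and the denominator together. Stopping is unlikely to be unrelated to response: lack of efficacy is one of the two reasons for a switch that the eCRF records (Protocol 7.6.5), and the sample-size simulation assumes that responders escalate less (Protocol 7.7). If patients not in LDA leave faster, those who remain are increasingly responders, and the plotted rate climbs with no change in anyone's disease.

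What is at stake is interpretation. The protocol states an interest in clinical effectiveness in usual care (7.12). A reader who takes the month-24 figure as the chance that a patient starting tofacitinib will be in LDA two years later would be misled, and nothing in the planned LDA and remission tables would correct that reading.

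**Working it through.** The documents give no expected LDA or remission rate over time and no rate of stopping tofacitinib, so there is no planned figure to reproduce. The check asks what the planned statistic shows when no patient's status ever changes.

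**Inputs**

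- Share in LDA, p = 0.20: planning value for the DAS28 criterion, Protocol 7.7. It is used here as a constant share of responders.
- Hazard ratio for leaving, LDA against non-LDA. Protocol 7.7 assumes escalation coefficients of -0.288 for LDA and -2.303 for a DAS28 change above 1.8, so exp(-0.288) = 0.75 and exp(-2.303) = 0.10. These are ratios for escalation, borrowed for stopping. The 0.10 belongs to the DAS28-change criterion and not to LDA.
- Share of non-LDA patients who have stopped by month 24, d: **assumed**, 20% to 60%.
- N = 1500 (Protocol 7.2), with complete scores while on drug.

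**Formulas**

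- Still on drug at month 24: S0 = 1 - d for non-LDA patients, and S1 = S0^HR for LDA patients.
- On-drug rate, as planned: p·S1 / (p·S1 + (1 - p)·S0).
- Fixed-denominator rate, with a stop counted as non-response: p·S1.

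**Worked case, d = 50%, HR = 0.10.** S0 = 0.50 and S1 = 0.50^0.10 = 0.933. In LDA on drug: 0.20 × 0.933 = 0.187 (280 of 1500). Not in LDA on drug: 0.80 × 0.50 = 0.400 (600 of 1500). The on-drug rate is 280/880 = 31.8% and the fixed-denominator rate is 280/1500 = 18.7%.

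**Month-24 results (LDA status constant at 20%)**

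| d | HR 0.75: on-drug | HR 0.75: fixed | HR 0.10: on-drug | HR 0.10: fixed | HR 1: on-drug |
|---|---|---|---|---|---|
| 20% | 20.9% | 16.9% | 23.4% | 19.6% | 20.0% |
| 30% | 21.5% | 15.3% | 25.6% | 19.3% | 20.0% |
| 40% | 22.1% | 13.6% | 28.4% | 19.0% | 20.0% |
| 50% | 22.9% | 11.9% | 31.8% | 18.7% | 20.0% |
| 60% | 23.9% | 10.1% | 36.3% | 18.2% | 20.0% |

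An intermediate ratio of 0.5 (assumed) gives an on-drug rate of 21.8% to 28.3% over the same range of d.

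**Path over time, d = 50%, HR = 0.10**, start and then months 3 to 24: 20.0, 21.3, 22.6, 24.0, 25.5, 27.0, 28.5, 30.1, 31.8%. In a table this would look like steady improvement.

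**Controls.** With equal exit the on-drug rate is flat. If LDA patients leave faster (HR 1.5, d = 50%), it falls to 15.0%. The direction of the bias therefore depends on who leaves. The fixed-denominator rate never rises here, but it falls although nobody worsens, because it also measures persistence on the drug.

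**The case against.** The strongest reply is that the on-drug rate is exactly what the protocol asks for. Section 6.1.2 words the endpoint for patients on tofacitinib, the SAP follows it openly, and these are descriptive secondary endpoints with no test or decision attached (SAP Section 5). This stands: the planned rate is a legitimate summary and not a departure from the protocol.

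The second reply is that other outputs fill the gap. Drug survival (SAP 7.1.2.10) gives the share still on drug, and multiplying the two recovers the fixed-denominator figure: in the worked case 880/1500 × 31.8% = 18.7%. That works only when every on-drug patient has a score. It also meets a mismatch of definitions, since a pause removes a patient from the SFAS but is not a termination in drug survival. The patient numbers per time point in SAP 9.2.1 come with reasons for leaving the study; they are not specified as numbers on drug with a score. The subgroups in SAP 6.6 depend on sufficient numbers, are mostly defined by what happens after baseline, and still use on-drug data only.

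Three stronger readings are tempting and are not supported.

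- **That the protocol already names this bias.** Protocol 7.12 says "there is a potential risk of bias due to missing outcome data", but its examples are a CRP not measured and a questionnaire not completed. Patients who stop are followed to month 24 (Protocol 7.1, 7.5.1.4); their data are excluded by the endpoint's definition and are not missing.
- **That the rates will rise.** They rise only if non-responders leave faster than responders.
- **That the rise is large.** One can build a steep case: 45% responders, with 15% of responders and 70% of non-responders stopping, gives 48% at month 3 and 70% at month 24. None of those three inputs is in the documents. In that case LDA among all starters stays at 45% by construction; what falls from 44% to 38% is the share both on tofacitinib and in LDA.

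**Conclusion.** The point holds as a limit on interpretation, with a cheap supplement as the answer. The planned rates describe patients still on tofacitinib at each visit. Their trend cannot be read as the course of response in patients who start it, because selective stopping alone can produce a rise, and no planned LDA or remission rate shows how much of the trend is selection.

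The size is open. With 20% in LDA, fixed status and an assumed 20% to 60% of non-LDA patients stopping, the month-24 rate is inflated by about 1 to 4 points at a ratio of 0.75 and about 3 to 16 points at 0.10, and by nothing if exit is equal. The lower ratio is the plan's value for a different response criterion, and both approximate stopping by escalation, which can occur while tofacitinib continues. The primary analysis is not affected.

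**What to change.** 1. Keep the on-drug rate as the planned endpoint.
2. For each LDA and remission definition, add a supplementary rate with all FAS patients as denominator, counting termination of tofacitinib as non-response. Label it *on tofacitinib and in LDA* (or *in remission*), so that it is not taken as disease activity in all starters. Note that the FAS requires a post-baseline visit (SAP 6.2) and so is close to, but not exactly, all starters.
3. State a separate rule for FAS patients who are on drug without a score, paused, or lost to follow-up. For example, show the rate once with them counted as non-response and once with them excluded. Visits are not mandatory, so this group may not be small.
4. Print the number on drug and the number with data at each visit.
5. Reconcile the SFAS label in SAP 9.2.3 with the FAS label in SAP 9.2.6, and add a sentence that the on-drug trend is conditional on remaining on treatment.

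Cost: no new data, since stop dates and scores are already collected, and a little more table work than one extra column because of item 3. The added figure will be less favourable, and it mixes persistence with response, which is why it belongs beside the on-drug rate and does not replace it.

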9.2.3.3 RATE OF REMISSION

Each definition of Remission (Section 7.1.2.3) will be presented as in Section 9.1.4, using the SFAS, only including data when patients were taking tofacitinib. Missing data will not be imputed (as per Section 8.2).

9.2.3.4 CHANGE FROM BASELINE IN DAS28-4 (ESR) AND DAS28-4 (CRP)

Change from baseline in DAS28-4 (ESR) and DAS28-4 (CRP) will be presented and analysed as in Section 9.1.3, using the SFAS, only including data when patients were taking tofacitinib. Missing data will not be imputed (as per Section 8.2)

9.2.3.5 CHANGE FROM BASELINE IN DURATION OF MORNING STIFFNESS

Duration of morning stiffness will be presented as in Section 9.1.3, using the SFAS, only including data when patients were taking tofacitinib. Missing data will not be imputed (as per Section 8.2)

9.2.3.6 CHANGE FROM BASELINE IN FFBH

Change from baseline in FFBH score will be presented and analysed as in Section 9.1.3, using the SFAS, only including data when patients were taking tofacitinib. Missing data will not be imputed (as per Section 8.2)

9.2.3.7 RATE OF FUNCTIONAL REMISSION

Rate of Functional Remission (Section 7.1.2.7) will be presented as in Section 9.1.4, using the SFAS, only including data when patients were taking tofacitinib. Missing data will not be imputed (as per Section 8.2).

9.2.3.8 CHANGE FROM BASELINE IN EQ-5D

Change from baseline in EQ-5D score (Section 7.1.2.8) will be presented and analysed as in Section 9.1.3, using the SFAS, only including data when patients were taking tofacitinib.

9.2.3.9 CHANGE FROM BASELINE IN FACIT-FATIGUE

Change from baseline in FACIT-FATIGUE score (Section 7.1.2.9) will be presented and analysed as in Section 9.1.3, using the SFAS, only including data when patients were taking tofacitinib.

9.2.3.10 DRUG SURVIVAL STATUS OF TOFACITINIB

Time to cease taking tofacitinib (drug survival) will be analysed as per Section 9.1.2, using the SFAS. Missing data will not be imputed (as per Section 8.1).

9.2.3.11 PATIENT'S SATISFACTION WITH DRUG TREATMENT

The Patient satisfaction is measured through a 5-point likert question asked at each visit and will be presented as in Section 9.1.5, using the FAS. At each visit, Visit X, only those who remained on tofacitinib at the previous visit, Visit X-1, will be presented. At each visit the satisfaction will be summarised split by those who remain on tofacitinib at Visit X and those who stop taking tofacitinib at Visit X.

9.2.4 SAFETY ANALYSES

- *Adverse events will be summarized according to Pfizer standards.*

Two sets of 'All Causality' and 'Treatment Emergent' adverse events will be summarised:

The first set will contain adverse event data for subjects while they were taking tofacitinib either as a monotherapy or in combination with MTX (patients will be included in this group if they have taken MTX at any point in the study in combination tofacitinib regardless of duration). This AE table will summarise AEs under one treatment heading

for tofacitinib (which includes monotherapy and combination therapy with MTX).. A drug lag of 28 days will be used to assign treatment emergence to tofacitinib. The second set will contain treatment emergent adverse events, which are related to tofacitinib and reported in a separate table.

Adverse events which occurred under another DMARD, following cessation of Tofacitinib, will only be listed and presented in a separate listing. AEs, which starts on the first day of a new treatment, e.g. Enbrel will be assigned to tofacitinib if the AE is within 28 days of tofacitinib. For non-Tofacitinib therapies a drug lag of 0 days will be applied. The AE will hence, also appear in the listing for other DMARDs as the AE started after the initiation of Enbrel. Therefore, any event which occurs during a 28 day lag of discontinuing tofacitinib will appear under tofacitinib in the tables and listings, and under the new treatment in the DMARD listing.

An all AE listing will show all AEs, individual rheumatologic therapies that are linked to the AE and whether the AE is tofacitinib treatment emergent.

Treatment labels for reporting adverse events:

Primary Adverse event table to assess AEs during tofacitinib treatment:

tofacitinib

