6.1. Endpoints

6.1.1. Primary Endpoint:

Impact of the following factors on the number of treatment escalations of Tofacitinib patients in 24 months

- a. DAS28-4 with Erythrocyte Sedimentation Rate (ESR)
- b. Δ DAS28-4 (ESR)
- c. Physician Global Assessment of Arthritis
- d. Patient's Assessment of Arthritis Pain
- e. Patient's satisfaction with drug treatment
- f. Patient's Global Assessment of Arthritis

Treatment escalation in this study is defined as a switch to another DMARD or combination of DMARDs when compared to the last visit.

6.1.2. Secondary Endpoints:

- a) Time to first treatment escalation
- b) Rate of Low Disease Activity (LDA) over time of patients on Tofacitinib (in combination therapy or monotherapy), as assessed by: Simplified Disease Activity Index (SDAI) \leq 11; Clinical Disease Activity Index (CDAI) \leq 10; DAS 28-4 (ESR) \leq 3.2 and DAS28-4 with C-reactive Protein (CRP) \leq 3.2.
- c) Rate of remission over time of patients on Tofacitinib (in combination therapy or monotherapy), as assessed by: American College of Rheumatology (ACR)-EULAR Boolean remission criteria; SDAI \leq 3.3; CDAI \leq 2.8; DAS 28-4 (ESR) $<$ 2.6 and DAS28-4 (CRP) $<$ 2.6
- d) Change from baseline over time of patients on Tofacitinib (in combination therapy or monotherapy) in DAS 28-4 (ESR) and DAS 28-4 (CRP)
- e) Change from baseline of duration of morning stiffness over time of patients on Tofacitinib (in combination therapy or monotherapy)

- f) Change from baseline in the Functional Ability Questionnaire Hannover (FFbH) over time of patients on Tofacitinib (in combination therapy or monotherapy)
- g) Rate of patients with functional remission in FFbH (FFbH > 83%) over time of patients on Tofacitinib (in combination therapy or monotherapy)
- h) Change from baseline in a self-report questionnaire (a quality of life instrument) developed by the European Quality of Life (EuroQoL) Group (EuroQoL EQ-5D) over time of patients on Tofacitinib (in combination therapy or monotherapy)
- i) Change from baseline in Functional Assessment of Chronic Illness Therapy (FACIT)-Fatigue scale over time of patients on Tofacitinib (in combination therapy or monotherapy)
- j) Drug survival at month 12, 24 of patients on Tofacitinib (in combination therapy or monotherapy)
- k) Patient's satisfaction with Tofacitinib treatment (in combination therapy or monotherapy) over time

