3.2.1.1 TREATMENT LABEL FOR SECONDARY ANALYSIS

tofacitinib (in Monotherapy or in Combination with MTX)

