7.3.3 POTENTIAL CONFOUNDERS TO BE INCLUDED IN THE PRIMARY ANALYSIS

A number of potential confounders will also be included in the primary analysis and all sensitivity analyses:

- Age at baseline
- Gender
- Duration of disease at baseline
- Indicator of tofacitinib dose
 - 1 if recommended dose of 5mg per day (i.e. TofInterval = BID),
 - 0 if reduced dose of 2.5mg per day (i.e. TofInterval = Daily).
- Poor prognostic factors (PF) indicator (1 if at least one Poor PF is present, 0 otherwise)
- Indicator of dose of MTX or combination partner (1 if increase in dose since last visit, 0 otherwise)
- Indicator of dose of Glucocorticoids (1 if increase in dose since last visit, 0 otherwise)
- Whether patient on 2nd or 3rd line treatment (see below)

A patient is defined as on 2nd line treatment if they were prescribed only csDMARDs prior to enrolling in the study.

A patient is defined as on 3rd line treatment if they were prescribed bDMARDs prior to enrolling in the study.

For a list of the medications considered to be csDMARDs and bDMARDs please see the eCRF.

- Indicator of tolerability issues (1 if treatment termination due to tolerability issues, 0 otherwise).
- Indicator of efficacy issues (1 if treatment termination due to efficacy issues, 0 otherwise).
- Incidence of the following comorbidities documented at the baseline visit (a term will be fitted for each comorbidity with the value 1 if the comorbidity is recorded for a patient or 0 otherwise):
 - Ischemic cardiovascular disease
 - Malignancies
 - Infections
 - Gastro disease
 - Osteoporosis
 - Depression

Any other variables observed to be potential confounders will also be investigated.

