12.1.2 DEFINITION OF TREATMENT ESCALATIONS

Table 11.2 provides an overview of all possible treatment switch combinations relevant for the analysis of the primary endpoint and defines the type of escalations, e.g., whether the treatment switch relates to a step-up, step-down or termination.

Table 12.2: Definition of treatment escalations

Therapy*	Mono Tofa	Mono tsDMARD	Mono csDMARD	MonoTNFi	Mono bDMARD	Combo+ csDMARD	Combo tsDMARD +csDMARD	ComboTNFi +csDMARD	Combo bDMARD+ csDMARD	Therapy Stop
MonoTofa	-	Step-up		Step-down	Step-up	Step-up	Step-up	Step-up	Step-up	Treatment termination
Mono tsDMARD	Step-up	Step-up if different tsDMARD		Step-down	Step-up	Step-up	Step-up	Step-up	Step-up	Treatment termination
Mono csDMARD	Step-up	Step-up	Step-up if different csDMARD		Step-up	Step-up	Step-up	Step-up	Step-up	Treatment termination
MonoTNFi	Step-up	Step-up		Step-down	Step-up if different TNFi	Step-up	Step-up	Step-up	Step-up	Treatment termination
Mono bDMARD	Step-up	Step-up		Step-down	Step-up	Step-up if different bDMARD	Step-up	Step-up	Step-up	Treatment termination
Combo+ csDMARD	Step- down	Step-up		Step-down	Step-up	Step-up	Step-up if different csDMARD	Step-up	Step-up	Treatment termination
Combo tsDMARD +csDMARD	Step-up	Step-up if different tsDMARD; Step-down otherwise		Step-down	Step-up	Step-up	Step-up if different tsDMARD or csDMARD	Step-up	Step-up	Treatment termination
Combo TNFi + csDMARD	Step-up	Step-up		Step-down	Step-down, if same TNFi, Step-up if different TNFi	Step-up	Step-up	Step-up if different csDMARD/TN Fi	Step-up if different bDMARD or csDMARD	Treatment termination
Combo bDMARD+ csDMARD	Step up	Step up		Step down	Step up	Step down if same bDMARD; Step-up otherwise	Step up	Step up	Step up	Step up if different bDMARD or csDMARD
*) Definitions:			Mono tsDMARD= Monotherapy any tsDMARD other than Tofa Mono csDMARD= Monotherapy any csDMARD Mono TNFi= Monotherapy any TNFi Mono bDMARD= Monotherapy any bDMARD other than TNFi Combo Tofa= Combination therapy tofacitinib with any csDMARD Combo csDMARD= Combination therapy tofacitinib + any csDMARD				Combo tsDMARD + csDMARD= Combination therapy tsDMARD other than tofacitinib + any csDMARD Combo TNFi + csDMARD= Combination therapy any TNFi+ any csDMARD Combo bDMARD + csDMARD= Combination therapy bDMARD other than TNFi+ anycsDMARD			

PPD

PPD

PPD

LEGAL DISCLOSURE

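### SAP 9.2.4 describes the main tofacitinib AE table as monotherapy or MTX combination only, so read literally it omits events on tofacitinib with another csDMARD

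*SAP*

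**What the plan says.** SAP 9.2.4 opens its description of the AE outputs with: "The first set will contain adverse event data for subjects while they were taking tofacitinib either as a monotherapy or in combination with MTX". A bracket then brings patients in if they took MTX with tofacitinib at any point. The single table heading is explained in the same terms: "for tofacitinib (which includes monotherapy and combination therapy with MTX". The section goes on: "A drug lag of 28 days will be used to assign treatment emergence to tofacitinib", and for the other set: "The second set will contain treatment emergent adverse events, which are related to tofacitinib and reported in a separate table". Neither of these sentences names a partner drug. An all-AE listing is also planned, and the label given at the end for the primary AE table is simply tofacitinib.

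The label for the secondary analyses in SAP 3.2.1.1 carries the same restriction: "tofacitinib (in Monotherapy or in Combination with MTX". The sequence-of-therapy groups in 3.2.1.2 and 6.6 likewise know only monotherapy and MTX.

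Other parts of the plan are wider. The footnote to the switch table in SAP 12.1.2 reads "Combo Tofa= Combination therapy tofacitinib with any csDMARD". SAP 7.3.3 lists as a confounder "Indicator of dose of MTX or combination partner". The Protocol's secondary endpoints (6.1.2) are worded "over time of patients on Tofacitinib (in combination therapy or monotherapy", with no partner named.

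**The concern.** The plan expects patients to take tofacitinib with csDMARDs other than MTX and classifies such regimens for the primary endpoint. The section that builds the main safety table does not mention them. A programmer who follows the MTX wording would drop on-drug events from the all-causality table. A programmer who follows the Safety Analysis Set would keep them. One SAP could therefore yield two different main safety tables. The literal version would understate events on tofacitinib in a study whose safety population is meant to be everyone treated.

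**Working it through.** No arithmetic applies to the contradiction itself, so the check compares the sections.

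1. **Can the regimen occur under the plan?** Yes. SAP 7.1.1 lists adding DMARDs to current therapy among the changes recorded on the eCRF. SAP 12.1.2 allows any csDMARD as partner. Protocol 7.1 leaves therapy to the treating physician. SAP 7.1.1 also says patients begin on monotherapy or with MTX, so on the SAP's own account the regimen arises only after baseline.

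2. **Where would an event on tofacitinib plus a non-MTX csDMARD go under SAP 9.2.4?**

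| Output | Entry condition | Event enters? |
|---|---|---|
| First AE set (main all-causality table) | On monotherapy or with MTX | Not on the literal text |
| Second AE set | Treatment emergent and related to tofacitinib | Only if judged related |
| Other-DMARD listing | On another DMARD after tofacitinib has stopped | No, tofacitinib is still being taken |
| All-AE listing | Every AE | Yes |

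3. **Is the literal result coherent?** No, for two reasons. A related event could stand in the second set and be absent from the all-causality table, which should contain it. And an event that starts on a new drug within 28 days of stopping tofacitinib is counted under tofacitinib, while an event during continuing tofacitinib treatment would not be, because of the partner drug.

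4. **Does the MTX bracket settle the matter?** No. It selects patients by whether they ever took MTX with tofacitinib, whereas the sentence around it selects time on a regimen. A patient who moved from tofacitinib with MTX to tofacitinib with another csDMARD might be admitted by the bracket. A patient who moved there from monotherapy would not be.

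5. **Which safety population applies?** SAP 6.4 and Protocol 7.9.1 base all safety reporting on patients with at least one tofacitinib dose, with no condition on partner.

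6. **Are secondary data lost?** Not from the overall tables. SAP 6.3 counts a patient as on tofacitinib unless it has been terminated or paused. The note in SAP 9.2.3 keeps all data collected on tofacitinib, whatever the treatment sequence. The label in 3.2.1.1 is narrower than the data it heads.

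7. **Are the subgroups affected?** Yes. A patient who goes from monotherapy to tofacitinib plus another csDMARD fits none of the four sequences in SAP 6.6. The fallback grouping by 60% of observation time has no group for time on that combination either. SAP 9.2.6 applies the sequence subgroup to nine secondary outcomes.

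8. **How large is the effect on the AE table?** Let *f* be the share of on-tofacitinib time spent with a non-MTX csDMARD, and *r* the AE rate on that regimen divided by the rate on all other tofacitinib regimens. On the literal reading the share of on-drug events omitted is *f r* / (*f r* + 1 − *f*), which equals *f* when *r* = 1. The documents give neither *f* nor *r*, so no figure can be put in.

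**The case against.** The best defence is that exclusion is only one reading of SAP 9.2.4. The Safety Analysis Set can be read as governing the section. The 28-day rule depends on tofacitinib alone, the final label is tofacitinib, and a heading that includes the MTX combination need not be confined to it. The definitions in 12.1.2 and 7.3.3 serve the primary endpoint and its model, not safety reporting. Subgroups need not cover every patient, and SAP 6.6 makes them conditional on sufficient numbers.

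Most of this stands. It shows that inclusion is probably what was intended. It does not remove the MTX limit, which 9.2.4 states twice in describing the main set, with no sentence bringing other partners in.

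A reader might also infer that these events appear in no output, or that on-drug data are missing from the secondary tables. The documents support neither. The all-AE listing takes every event, the second set has no MTX limit, and the SFAS rule keeps every visit on tofacitinib.

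**Conclusion.** The point holds for the main AE table as an internal contradiction that, followed literally, leaves that table incomplete. For the secondary endpoints it holds only for the label in SAP 3.2.1.1 and for the sequence subgroups. The size is unknown. It is zero if the table is programmed on the inclusive reading or if nobody reaches such a regimen. Otherwise it is every event on that regimen, subject to how the MTX bracket is applied. Any stated percentage would be an assumption without an anchor in the documents. That the gap concerns only regimens reached after baseline rests on taking SAP 7.1.1 at its word about starting therapy. The wording should be settled before the final tables are run, since it decides the content of the main safety output.

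**What to change.** - **SAP 9.2.4:** state that the tofacitinib AE table counts every AE from the first tofacitinib dose to 28 days after the last, whatever the partner drug. Delete the bracket on MTX use at any point, and drop MTX from the explanation of the heading.
- **SAP 3.2.1.1:** reword the label to match the SFAS rule, that is, tofacitinib alone or in any combination.
- **SAP 3.2.1.2 and 6.6:** either add a category for other csDMARD partners, in both the four-sequence and the 60% version, or state that such patients are not classified. Keeping the MTX groups as they are preserves what those groups describe.

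The cost is a few lines of SAP text and matching table headings. An added subgroup category needs a little programming. No new data are needed, since Protocol 7.6.5 already records DMARD treatment at each visit, and patient care is untouched.
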